We chose the sample size (36 subjects completing the training per group) to have good power to detect moderate effects of the TMR at the post-training assessment. More specifically, with a sample size of 36 per group we will have 85% power to detect a difference between the groups if the mean changes in the two groups differ by 0.72 standard deviations (i.e., an "effect size" of 0.72). This calculation is based on the performance of a two-sided .05-level two sample t-test. This is a conservative projection of the power because the actual analysis will be based on a mixed effects model for repeated measures, and will be slightly more powerful than a t-test. Note an effect size of 0.72 is considerably smaller than the effect sizes we observed for the response variables in our pilot data as shown in the following table. Thus, we believe the study is adequately powered even if our findings in the proposed study are somewhat less striking than those observed in our pilot study. If we want to control the experiment-wise type-1 error rate at 0.05 we will have to test each hypothesis at the 0.007 level (to adjust for multiple comparisons). This will result in 85% power to detect on effect size of 0.90. Note that this detectable effect size is still considerably smaller than the effects observed in our pilot study for all variables except gait velocity.
- 2 * Provide the plan for data analysis. Include in the description the types of comparisons that are planned (e.g., comparison of means, comparison of proportions, regressions, analysis of variance, etc.), which is the primary comparison/analysis, and how the analyses proposed will relate to the primary purposes of the study:

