2.3 Statistical Model. To estimate the impact of TMR vs TR, for each outcome, we will fit the following model:

E(Outcome)= β_0 + β_1 F1 + β_2 F2 + β_3 F3 + β_4 F1(TMR) + β_5 F2(TMR) + β_6 F3(TMR) + β_6 F3(TMR) + β_6 Covariates)

where F1, F2, and F3 are indicators for the three follow-up measures, and TMR is an indicator that the patient was in the TMR group. In this model, β_4 , β_5 , and β_6 stand for the difference between TMR and TR at each of the three follow-up time points. The primary analysis will be based on β_4 . This model will be fit using restricted maximum likelihood, allowing for different variancs at each time point, and different covariances between any two time points (this is sometimes referred to as an "unstructured" variance/covariance assumption). We will allow a different variance/covariance structure in each intervention group. However, if the differences in the estimated variance/covariance structures are not statistically significant (based on a likelihood ratio test), we will assume a common variance/covariance structure in the final model.

This model will provide valid inference if the distribution of outcomes does not markedly depart from normality. If an outcome appears to depart from normality by exhibiting a great deal of positive skewness (e.g., skewness coefficient greater than 3.0), I will fit the above model using a log-tranformed version of the outcome.

2.4 Covariates. Covariates will be included in the model if they are statistically significant (p<0.05) predictors of the outcome. This will reduce residual variation and increase power. Up to 3 covariates will be included in the model based on the strength of their statistical significance, chosen in a forward stepwise manner. Covariate will be chosen from the following candidate variables.

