Time Since Stroke Age Sex Wearing an AFO Non-AFO AD SIS mobility Baseline Gait Velocity (cm/sec) Baseline Peak Paretic DF Swing Angle (deg) Baseline Paretic DF Angle at Foot Contact (deg) Baseline Paretic A-P Propulsion in Late Stance (N-s) Baseline CoP Sway Area (cm2) Baseline Standing asymmetry (NP/P vertical forces) Baseline Peak Paretic A-P force during gait initiation (N) **2.5 Impact of Missing Outcomes.** The methods described above will result in unbiased estimates of the impact of being assigned toTMR assuming that the data are missing at random, given all observed data. That means, essentially, that conditional on all observed outcomes, the distribution of the missing outcomes is not different than the distribution of the observed outcomes. However, if there are departures from the missing-at-random assumption (e.g., if those with the worst outcomes are the ones who fail to return for follow-up visits), then the estimated rates of improvement may be biased. Note, however, that the estimated treatment effect would only be biased if there were differential degrees of departure from the missing-at-random assumption in the two treatment groups.

The proposed approach is somewhat resistant to biases due to missing data because it is based on maximum likelihood estimation and takes into consideration all the observed data. Thus, for example, if a patient has missing outcomes for the second follow-up visit, but has been observed at other time points, the estimation of the outcomes at the second follow-up will be implicitly imputed based on the observed outcomes and the included covariates.

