3.0 Secondary Analyses

3.1 Intention to treat analysis of secondary outcomes. Similar analyses will be performed to explore the impact of TMR on the following secondary outcomes:

AIM 1

- Single support duration (Var="P-SS%")
- Double support duration (Var="DS%")
- Timing of peak fexion (Var="PK DF P-ank %cyc")
- Pareti foot vertical clearance (Var="p-foot clearance")
- Steps/day in two consecutive days (Var="48 hr Step Count ") (There seems to have been a lot of non-adherence regarding this measure and it may not be usable)
- Stroke Impact Scale (Var="SIS Mobility")

AIM 2

- coP trajectories of APAs during gait initiation by leg (Not measured)
- Berg Balance Scale (Var="Berg Balance")
- DGI scale (Var="DGI")
- ABC Scale (Var="ABC")

3.2 Per Protocol Analysis. In a secondary set of analyses, we will perform all of the above described analyses after including only those patients who attended at least 15 sessions in their assigned group. This results in an estimate of the causal impact of the TMR (relative to TM) among those willing and able to come to most of the sessions. We would expect to see a somewhat greater effect of TMR in this analysis because it will remove those who did not attend the TM sessions.

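### SAP 2.4 chooses covariates for each outcome by stepwise p-values and β4 is then tested as if they had been fixed; the error-rate cost is small, but the list should be set in advance

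*SAP*

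**What the plan says.** SAP 2.3 sets up one model per outcome: "for each outcome, we will fit the following model". It has an intercept, indicators for the three follow-ups, a TMR term at each follow-up, and covariates. The primary comparison is β4, the TMR term at the end of training.

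SAP 2.4 gives the covariate rule: "Covariates will be included in the model if they are statistically significant (p<0.05) predictors of the outcome". At most three enter, "included in the model based on the strength of their statistical significance, chosen in a forward stepwise manner". The list has 13 candidates: six clinical or demographic items and seven baseline gait and balance measures. The stated purpose is less residual variation and more power.

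The SAP does not say whether the TMR terms are in the model while covariates are being chosen. It plans no allowance for the selection (bootstrap or permutation) and no unadjusted sensitivity analysis. It gives no significance level for the treatment test. The Protocol's sample-size section does: "This calculation is based on the performance of a two-sided .05-level two sample t-test".

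Three related points:
- SAP 1.0 says that randomisation was blocked within two baseline gait-speed strata. The stratum is not on the candidate list, and continuous gait velocity is only a candidate.
- SAP 3.2 repeats every analysis in patients who attended at least 15 sessions.
- Three adjacent candidates, "Wearing an AFO Non-AFO AD SIS mobility", lack the Baseline label that the seven gait and balance measures carry. SIS Mobility is also the variable name of a secondary outcome in SAP 3.1.

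**The concern.** A forward search keeps the covariates that best explain the outcome in this particular sample. If β4 is then tested as though those covariates had been named beforehand, its standard error leaves out the variation due to the search. β4 is the primary comparison for every outcome, so its confidence interval could be too narrow and its 5% error rate exceeded.

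The rule also leaves the primary estimate open. Two analysts who differ on whether TMR is in the selection model can reach different covariate sets and different values of β4. The set may change between the intention-to-treat and per-protocol samples, so part of any difference between those results could come from changed adjustment. The primary model may also contain no term for the factor on which randomisation was stratified.

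**Working it through.** **1. The plan's own figure.** Inputs from the Protocol's sample-size section: 36 per group, effect 0.72 SD, two-sided 0.05. Power = Φ(d√(n/2) − z) = Φ(0.72×√18 − 1.960) = Φ(1.095) = 86.3%; the noncentral t gives 85.4%. At 0.90 SD and level 0.007: Φ(3.818 − 2.697) = Φ(1.121) = 86.9%; the noncentral t gives 84.7%. The stated 85% is reproduced in both cases. The documents give no type I error for the test after covariate selection, so that has to be simulated.

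**2. Which model to size.** SAP 2.3 has an intercept plus F1, F2 and F3. On follow-up rows alone F1 + F2 + F3 = 1 in every row, which duplicates the intercept, so the model could not be estimated. Baseline must therefore be a response row. The Protocol's analysis section likewise lists baseline among the repeated measures.

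**3. How often selection acts.** With 13 independent, unrelated candidates the chance that at least one enters first is 1 − 0.95^13 = 48.7%.

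**4. Mechanism, in a simpler model.** Single-visit ANCOVA, 36 per arm, 20,000 null trials per setting, simulation SE about 0.15 to 0.18 points:

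| Setting | Rejects at 5% | Mean SE / true SD |
|---|---|---|
| No covariates | 5.0% | 0.2351/0.2356 = 0.998 |
| Stepwise, unrelated candidates, TMR in | 6.2% | 0.2309/0.2432 = 0.949 |
| Same, TMR out | 4.8% | 0.2311/0.2319 = 0.997 |
| Stepwise, six moderate predictors, TMR in | 7.3% | 0.1990/0.2186 = 0.910 |
| Stepwise, three strong predictors, TMR in | 5.1% | 0.1517/0.1527 = 0.993 |
| Three covariates fixed in advance | 4.9% | 0.1518/0.1519 = 0.999 |

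With unrelated candidates and TMR in, the reported SE falls (0.2351 to 0.2309) while the true spread of the estimate rises (0.2356 to 0.2432). Across all settings the rate is 5.1% to 7.3% with TMR in and 4.8% to 5.3% with TMR out.

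**5. The SAP 2.3 form.** REML, common unstructured covariance, baseline as a response row. Three sets of simulated null trials with different assumed correlations, TMR in during selection:

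| Set | Stepwise | Comparator | Added by selection (points) |
|---|---|---|---|
| A, 72 patients, 10,000 trials | 5.89% | fixed pair 5.56% | 0.33 |
| A, 58 patients, 10,000 trials | 5.88% | fixed pair 5.47% | 0.41 |
| B, 72 patients, unrelated candidates, 10,000 trials | 5.31% | no selection, same data 5.16% | 0.15 (SE 0.10) |
| B, 72 patients, six predictors, 8,000 trials | 5.53% | no selection, same data 5.19% | 0.34 (SE 0.19) |
| C, 72 patients, 6,000 trials | 5.9–6.0% | fixed list or no covariates 5.7–5.8% | about 0.2 |

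With TMR out, set B gives 4.94% against 5.11% and 5.04% against 5.19%, so no inflation. In set B the ratio of mean SE to true SD is 0.1861/0.1884 = 0.988 and 0.1477/0.1507 = 0.980 with stepwise (TMR in). It is 0.1867/0.1888 = 0.989 with no selection.

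**6. Baseline as a covariate on follow-up rows.** This is not the SAP 2.3 form. Set A gives 6.29% − 5.02% = 1.27 points (72 patients) and 6.18% − 5.01% = 1.17 points (58 patients). Set C gives 0.3 to 0.7 points.

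**7. Stability and power.** In set A the most frequent covariate set appears in only 17% to 26% of repeated trials. Power at 0.45 SD with two good fixed predictors against stepwise is 83.6% and 83.5% (SAP 2.3 form), and 82.4% and 82.8% (follow-up rows). A weaker three-covariate list has 1 to 3 points less nominal power than stepwise.

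**The case against.** The strongest reply is that the rule is itself prespecified (candidates, threshold and cap) and that the harm in the planned model is close to simulation error. That is largely right. Several stronger claims that a reader might draw do not hold.

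- **That the 5% test runs at about 6% because of selection.** Excesses of a point or more come from single-visit or follow-up-row models, which SAP 2.3 does not specify. In the SAP 2.3 form, where rates do come near 6%, most of the gap above 5% is also there with a fixed list or no covariates.
- **That fixing the list restores exactly 5%.** In the SAP 2.3 form a fixed pair still rejects at 5.47% to 5.56% in set A. That part is not caused by selection and would remain.
- **That the SAP puts TMR in the selection model.** Covariates that enter the model of SAP 2.3 would naturally enter one that already holds TMR, but the text does not say so, and the inflation depends on it.
- **That different covariates for different outcomes are a flaw.** Outcomes have different predictors. In a randomised linear model, baseline covariates fixed in advance change the precision of β4, not what it estimates.
- **That a follow-up SIS Mobility value would be used as a covariate.** The Protocol collects the Stroke Impact Scale before training, and the item sits in a list of baseline characteristics. The missing label is an ambiguity only.

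What remains is that the selection is unaccounted for, its key detail is unstated, and the adjustment set is unstable.

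**Conclusion.** The concern holds in a modest form. β4 is tested as if a data-chosen covariate set had been fixed. If TMR is in the model during selection, this adds about 0.1 to 0.4 points to the type I error in the SAP 2.3 form. It adds about 0.3 to 1.3 points with baseline as a covariate on follow-up rows, and essentially none with TMR out.

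These sizes rest on assumptions that the documents do not supply: covariate strengths and correlations, visit correlations (0.65 to 0.75 in set A, 0.6 in set B), and 58 patients as a lower sample size. Sets A and B left the outcome's own baseline out of the candidates. Neither arm-specific covariance, which is the SAP's starting model, nor dropout was simulated in those sets.

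The case for change therefore rests less on the error rate than on three other points. The primary estimate cannot be fully determined from the SAP, the set can differ between the intention-to-treat and per-protocol samples, and the stratification factor can be missing from the primary model. The effect of that last omission was not sized.

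**What to change.** Replace the stepwise rule in SAP 2.4 with a short covariate list, fixed before outcomes are joined to arm and kept whatever the p-values.

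- Always include the baseline gait-speed stratum used in randomisation. For the gait velocity outcome, say how it sits beside that outcome's own baseline.
- Add one or two listed baseline candidates, for example AFO use.
- Fix the list outcome by outcome, and use the same list for a given outcome in the intention-to-treat and per-protocol analyses. One list for all outcomes that also avoids each outcome's own baseline could hold no gait or ankle measure, because every such candidate is the baseline of a main outcome in SAP 2.1.
- State that AFO, AD and SIS mobility are baseline values.
- Keep the stepwise model as a labelled sensitivity analysis, and say whether TMR is in the model during its selection.

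The cost is a few lines of SAP text and no new data. The downside is that a poorly chosen list may lose about 1 to 3 points of power; a well-chosen pair lost essentially none in the simulations.

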Official Title: Adaptive Ankle Robot Control System to Reduce Foot-drop in Chronic Stroke

NCT02483676

April 12, 2019

Statistical Analysis Plan for the study of Ankle Robot to Reduce Foot Drop in Stroke

This document lays out the analysis plan we intend to use for the study of whether robot-assisted treadmill training will result in greater improvements in gait and balance among chronic stroke survivors with foot drop impairment.

1.0 Brief description of the design of the parent study.

After baseline data collection, eligible patients were randomized to receive either treadmill with anklebot (TMR) or standard treadmill TM alone. Randomization was based on permuted blocks in two strata defined by baseline gait speed. Subjects in each group were be expected to attend 3 sessions per week for six weeks. Follow-up data collection will occur at the end of the training session. Durability of the improvements will be measured by also collecting data 6 weeks and 6 months after the end of the intervention. The primary outcomes will be the outcomes measured immediately after the end of training.

2.0 Statistical Test of the Primary Hypotheses.

2.1 Outcomes. The main outcomes to be considered will be::

AIM 1

- peak DF swing angle (Var="Pk DF P-ank) (Primary Outcome)
- DF angle at foot strike (Var="AIC") (2nd Primary Outcome)
- Mean Gait Velocity (Var="Prefered Gaid Velocity w/o AD")
- A-P GRF Propulsion (Var="AP impulse")

AIM 2

- Extent of Postural Sway (Var="EO Sway Area" or "EC Sway Area")
- Peak paretic A-P forces during push-off nonparetic gait initiation (Primary Outcome for Aim 2. (Var="Gait Initiation Peak NP A-P force") (Not collected for last 10-15 patients)

All these outcomes will be treated as quantitative random variables.

2.2 Analysis Sample. The primary analysis will be based on the principle of intention to treat. That is, in the analysis, patients will be included in the group to which

they were randomized, irrespective of whether they actually received the intervention. This provides anunbiased estimate of the causal impact of assigning a patient to TMR vs. assigning them to TR. The principle of intention-to-treat will be violated to the degree that outcomes for some patients at some timepoints are missing. The implications of missing data and how we will handle that are discussed below. Secondary analyses (described below) will be performed to using different analysis samples to estimate different causal parameters.

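### A candidate covariate that was apparently not collected for the last 10-15 patients could, if selected, drop those patients from models of outcomes they do have

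*SAP*

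**What the plan says.** SAP 2.3 gives one model form, fitted by restricted maximum likelihood to each outcome, with a term for covariates. SAP 2.4 fills that term by forward stepwise selection, up to three variables: "Covariates will be included in the model if they are statistically significant (p<0.05) predictors of the outcome". There is a single list of 13 candidates, not tailored to the outcome, and its last entry is "Baseline Peak Paretic A-P force during gait initiation (N". SAP 3.1 plans similar analyses for the secondary outcomes.

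SAP 2.1 attaches a note to the Aim 2 primary outcome, the peak A-P force in gait initiation: "Not collected for last 10-15 patients". No such note is attached to the Aim 1 outcomes: peak DF swing angle, DF angle at foot strike, gait velocity and A-P propulsion.

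SAP 2.2 makes intention to treat the primary analysis and concedes departures from it only where outcomes are missing. SAP 2.5 is likewise confined to missing outcomes. It says the likelihood approach "takes into consideration all the observed data", and it describes a missing outcome as implicitly imputed from the observed outcomes and the included covariates. The protocol's data analysis plan says that SAS PROC MIXED lets subjects with incomplete data be included. Neither document gives a rule for a missing baseline covariate.

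**The concern.** A likelihood mixed model copes with a missing outcome by using the patient's other visits. It does not do this for a missing fixed-effect covariate: standard software omits every row for which the covariate is absent. A baseline covariate is constant within patient, so a missing value removes the whole patient.

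If this candidate were chosen for peak DF swing angle, the last 10-15 patients would leave the Aim 1 primary model although the SAP gives no sign that their DF angles are missing. SAP 2.4 introduces covariates to reduce residual variation and raise power, and here the step could lower power instead. It would also open a route out of the intention-to-treat sample that SAP 2.2 does not acknowledge. The issue is distinct from the Aim 2 outcome being missing. For the Aim 2 primary itself, these patients contribute no outcome anyway, so nothing further is lost there.

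**Working it through.** **Inputs.** The protocol's sample size section gives "36 subjects completing the training per group", so 72 in all. It claims "85% power to detect a difference between the groups if the mean changes in the two groups differ by 0.72 standard deviations", from a "two-sided .05-level two sample t-test". SAP 2.1 gives 10 to 15 patients without the measure. The protocol's Participant Selection section gives 100 to be enrolled. Neither document states the number randomised, so 72 and 100 serve as a range.

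**The plan's own figure.** Noncentral-t power with 36 per group, d = 0.72 and two-sided alpha 0.05 is 85.4%, so the stated 85% reproduces. The protocol also considers having to "test each hypothesis at the 0.007 level", with detectable effect 0.90. That gives 84.7% and reproduces too.

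**Patients and rows lost.** 10/72 = 13.9% and 15/72 = 20.8%, leaving 62 or 57. With up to four visits each, 10 patients are up to 40 of 288 rows and 15 are up to 60. From 100: 10% and 15%, leaving 90 or 85.

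**Standard error before any covariate gain.** The ratio is sqrt(N/n).
- 72: sqrt(72/62) = 1.078 and sqrt(72/57) = 1.124, so +7.8% to +12.4%.
- 100: sqrt(100/90) = 1.054 and sqrt(100/85) = 1.085, so +5.4% to +8.5%.

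**Net of the gain from a covariate just reaching p<0.05.** Such a covariate explains R² = t²/(t² + n − 2) of the residual variance, and the net ratio is sqrt(N/n) × sqrt(1 − R²).

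| N | n left | t² | R² | Net ratio | Net change in SE |
|---|---|---|---|---|---|
| 72 | 62 | 4.001 | 6.3% | 1.078 × 0.968 | +4.3% |
| 72 | 57 | 4.016 | 6.8% | 1.124 × 0.965 | +8.5% |
| 100 | 90 | 3.949 | 4.3% | 1.054 × 0.978 | +3.1% |
| 100 | 85 | 3.956 | 4.5% | 1.085 × 0.977 | +6.0% |

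**Break-even.** Setting (1 − R²)/n = 1/N gives R² = 1 − n/N. This is 13.9% to 20.8% with 72 (partial r of 0.37 to 0.46) and 10% to 15% with 100. The p<0.05 entry rule admits covariates well below these values.

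**Power at d = 0.72, alpha 0.05, starting from 72.**
- 31/31: 79.6% without covariate gain. With d divided by sqrt(1 − R²): 82.1%.
- 28/29: 76.1% without covariate gain, 79.0% with it.

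At alpha 0.007 and d = 0.90, power without covariate gain falls from 84.7% to 77.0% or 72.2%.

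These are single-time-point t-test illustrations. The SAP 2.3 model has baseline in the response vector, up to four time points and an unstructured covariance, so the figures indicate size only.

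**The case against.** **The missing baseline is inferred.** The SAP 2.1 note is attached to an outcome. Its text describes a paretic force, while its variable label reads NP; the SAP 2.4 candidate is described as paretic. No passage says that baseline is missing. The inference is natural, because the note is per patient and the protocol repeats the same motor assessments at baseline and follow-up, but it stands as an inference.

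**Selection is not certain.** This is one of 13 candidates for at most three places. For the Aim 1 outcomes it competes with baseline DF angles, gait velocity and propulsion, which are closer constructs, and its own p-value comes from fewer patients. If it is not selected, the fitted Aim 1 model loses nobody on this account. A reader might infer that these patients would drop out of selection regardless, because some stepwise routines start from patients complete on all candidates. Neither document names a selection routine, so this is a possibility to close off and cannot be counted as a consequence of the plan.

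**The net figure uses a covariate at the entry threshold.** Selection ranks by significance, so a chosen covariate may explain more, and above the break-even value the net effect is a gain. In the other direction, the outcome's own baseline is already in the response vector and may absorb part of what the covariate would explain. The net figures are therefore approximate both ways.

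**Bias.** A reader might infer that removing the latest enrolled patients biases the treatment effect. The documents do not support that. The loss follows enrolment order, and SAP 1.0 describes permuted blocks within two gait-speed strata, so it should fall nearly evenly across arms.

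What remains is that the SAP records the incomplete collection of this measure and still offers its baseline for every outcome, with no rule for a missing covariate.

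**Conclusion.** The point holds in conditional form. If baseline gait-initiation force is missing for the last 10-15 patients and the variable is selected, those patients leave the affected models with all their observed outcomes. Only in that event would the intention-to-treat and all-observed-data statements of SAP 2.2 and 2.5 fail for that model; they are not untrue as the plan stands.

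The cost is precision, at the sizes worked out above. On the planned 72, power at d = 0.72 would fall from 85.4% to 79.6% or 76.1% before covariate gain, or to 82.1% or 79.0% with a threshold covariate. The power figures assume near-even loss across arms and the protocol's t-test setting. If the sponsor confirms that baseline was in fact collected for these patients, the concern about this candidate falls away and only the missing rule for absent covariates remains.

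**What to change.** First, confirm whether the baseline value is missing for the last 10-15 patients, and reconcile the paretic description with the NP label in SAP 2.1.

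Then, in SAP 2.4, remove baseline peak paretic A-P force during gait initiation from the candidate list for all outcomes. Gait-initiation force itself should be no exception: SAP 2.3 has indicators only for the three follow-ups, so the baseline value is already in the response vector and as a covariate would predict its own row.

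Add one sentence: candidates not collected by design for a block of patients are excluded; sporadically missing values of the remaining candidates are filled with the overall baseline mean, without using arm; and selection and final models are run on all randomised patients with observed outcomes.

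This takes a few lines of SAP text. The downside is the loss of one of 13 candidate covariates.
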